4.2.7.3 Subgroup summary

No subgroup summaries are planned.

4.2.7.4 ORR

The ORR will be based on the programmatically derived RECIST outcome using the investigator data.

ORR will be analyzed in terms of the proportion of responders out of the number of available patients per treatment arm. The associated 95% confidence intervals will also be provided using the Clopper-Pearson exact method for binomial proportions.

4.2.7.5 OS

The proportion of patients alive at 12 months will be reported. Kaplan-Meier plots and estimates will be produced at the time of summary.

4.2.7.6 DoR

DoR will be reported using summary statistics (n, median and quartiles) and KM plots to describe the duration of response in those patients with an initial response on study.

4.2.7.7 DCR

DCR will be presented as the proportion of patients with disease control, out of the number of patients available per treatment arm. The associated 95% confidence intervals will also be provided using the Clopper-Pearson exact method for binomial proportions.

4.2.7.8 Tumour shrinkage

The best absolute change in target lesion tumour size from baseline, and percentage change in target lesion tumour size from baseline will be summarised using descriptive statistics and presented at each time point by randomized treatment group.

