3. PRIMARY AND EXPLORATORY VARIABLES

3.1 Derivation of RECIST visit responses

All RECIST assessments, whether scheduled or unscheduled, will be included in the calculations. This is also regardless of whether a patient discontinues study drug.

For all patients, the RECIST version 1.1 (see further Appendix C of the CSP) tumour response data will be used to determine each patient's visit response. It will also be used to determine if and when a patient has progressed and also their best overall response.

The baseline tumour assessment is part of the screening procedures and should be performed within 28 days before the start of study treatment.

Prior to approval of CSP version 2.0, efficacy for all patients will be assessed by objective tumour assessments every 8 weeks (relative to the first dose) for the first 48 weeks, then every 12 weeks thereafter, until confirmed objective disease progression as defined by RECIST 1.1 (irrespective of the reason for stopping study drug and/or subsequent therapy). For patients who discontinue study drug due to toxicity or a reason other than confirmed progression of disease (PD), objective tumour assessments should be continued every 8 weeks for 48 weeks (relative to first dose) then every 12 weeks thereafter until confirmed objective disease

progression. If an unscheduled assessment is performed, and the patient has not progressed, every attempt should be made to perform the subsequent assessments at their scheduled visits. Patients on monotherapy AZD9291 will be assessed according to local practice until objective disease progression.

Disease progression requires confirmation, the confirmatory scan should occur preferably at the next scheduled visit and no earlier than 4 weeks after the initial assessment of PD in the absence of clinically significant deterioration. Study treatment will continue between the initial assessment of progression and confirmation for progression.

Progression would be considered confirmed if the following criteria are met:

- $\geq 20\%$ increase in the sum diameters of target lesions (TLs) compared with the nadir at 2 consecutive visits with an absolute increase of at least 5 mm.

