3.2.2 Objective response rate (ORR)

ORR (per RECIST 1.1 as assessed by the investigator) is defined as the number and percentage of patients with measurable disease with at least 1 visit response of CR or PR. Summaries will be produced based on both unconfirmed and confirmed response, where the response is confirmed at least 4 weeks later. ORR will be based on all randomised patients. Therefore, data obtained up until progression, or the last evaluable assessment in the absence of progression, will be included in the assessment of ORR.

A subject who goes off treatment without progression to receive a subsequent anti-cancer therapy, and then responds (CR or PR), will not be included as a responder in the ORR.

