3.2.5 Best overall response

Best overall response (BOR) is calculated based on the overall visit response from each RECIST assessment. It is the best response a patient has had following randomisation but prior to starting any subsequent anti-cancer therapy and prior to RECIST progression or the last evaluable assessment in the absence of RECIST progression and subsequent anti-cancer therapy.

Categorisation of BOR will be based on RECIST using the following response categories: CR, PR, SD, PD and NE.

BOR will be determined programmatically based on RECIST from the overall visit response at each visit using investigator assessment data including all data up until the first progression,

the start of any subsequent cancer therapy or the last evaluable assessment in the absence of progression.

For determination of a best response of SD, the earliest of the dates contributing towards a particular overall visit assessment will be used. SD should be recorded at least 16 weeks +/- 1 week, i.e. at least 119 days (to allow for the assessment window), after randomisation (i.e. study day 120). For CR/PR, the initial overall visit assessment which showed a response will use the latest of the dates contributing towards a particular overall visit assessment.

For patients whose PFS event is death, BOR will be calculated based upon all evaluable RECIST assessments prior to death.

For patients who die with no evaluable RECIST assessments, if the death occurs ≤ 17 weeks (i.e., 16 weeks + 1 week to allow for a late assessment within the assessment window) after randomisation, then BOR will be assigned to the progression (PD) category. For patients who die with no evaluable RECIST assessments, if the death occurs > 17 weeks (i.e., 16 weeks + 1 week) after the date of first dose then BOR will be assigned to the NE category.

Progression events that have been censored due to them being more than two missed visits after the last evaluable assessment will not contribute to the BOR derivation.

Summaries will be produced based on both confirmed and unconfirmed response.

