3.2.6 Tumour shrinkage

Tumour shrinkage will be assessed using RECIST 1.1 tumour response. The absolute change and percentage change from baseline in sum of tumour size at each assessment will be calculated. Tumour size is the sum of the longest diameters (SLD) of the TLs. The percentage change in SLD at each week for which data are available will be obtained for each subject taking the difference between the SLD at each week and the SLD at baseline divided by the SLD at baseline multiplied by 100 (i.e., $[\text{week } n - \text{baseline}] / \text{baseline} \times 100$). The change from baseline will be obtained for each subject taking the difference between the SLD at each week and the SLD at baseline (i.e., week n - baseline).

The best percentage change in SLD from baseline or the minimum increase from baseline in the absence of a reduction from baseline based on all post-baseline assessments prior to progression or start of subsequent anti-cancer therapy.

If best percentage change cannot be calculated due to missing data, a value of +20% will be imputed as the best percentage change from baseline in the following situations (otherwise best percentage change will be left as missing):

- If a subject has no post-baseline assessment and has died;
- If a subject has new lesions or progression of NTLs;
- If a subject has withdrawn due to PD and has no evaluable TL data before or at PD.

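### By-visit change in target lesion size has no cut at the start of subsequent anti-cancer therapy, although best percentage change, ORR and best overall response do (minor, exploratory endpoint)

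*SAP*

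**What the plan says.** **By-visit change.** SAP 3.2.6 states: "The absolute change and percentage change from baseline in sum of tumour size at each assessment will be calculated". It adds: "The percentage change in SLD at each week for which data are available will be obtained for each subject". Neither sentence sets an end point. SAP 4.2.7.8 then says that the best absolute change and the percentage change "will be summarised using descriptive statistics and presented at each time point by randomized treatment group".

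**Best percentage change.** The same section, 3.2.6, defines this as "based on all post-baseline assessments prior to progression or start of subsequent anti-cancer therapy". It gives no separate rule for best absolute change, which 4.2.7.8 also reports.

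**Response outputs.** On ORR, SAP 3.2.2 says: "A subject who goes off treatment without progression to receive a subsequent anti-cancer therapy, and then responds (CR or PR), will not be included". Such a patient is thus kept out of the ORR numerator. On best overall response, SAP 3.2.5 says: "It is the best response a patient has had following randomisation but prior to starting any subsequent anti-cancer therapy". Both also stop at progression.

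**Scanning.** SAP 3.1 brings all RECIST assessments into the calculations, whether or not study drug has stopped. Before approval of protocol version 2.0 it continues scans to confirmed progression, "irrespective of the reason for stopping study drug and/or subsequent therapy".

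**The concern.** One measure, target lesion size, is handled under two rules in the same section, and no reason is given. A patient may stop for toxicity without progression, start another cancer drug and be scanned again. That scan is left out of the patient's best percentage change, and a response on it does not count in ORR or best overall response. It still enters the by-visit table under the randomised arm. The by-visit value can then be lower than the value reported as the patient's best, and a reader of the study report could not reconcile the two outputs.

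Tumour shrinkage is one of the exploratory efficacy measures in SAP 1.1, for the combination and for monotherapy. What is at stake is whether a descriptive table for a small trial can be read correctly. The primary objective, which is safety, is not affected.

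**Working it through.** The SAP states no figure on this point, so there is none to reproduce. The check compares the rules and then illustrates the possible size.

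**Step 1. Which scans enter each output**

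| Output | SAP section | Stops at subsequent therapy? | Stops at progression? |
|---|---|---|---|
| Best percentage change | 3.2.6 | Yes | Yes |
| ORR | 3.2.2 | Yes | Yes |
| Best overall response | 3.2.5 | Yes | Yes |
| By-visit change | 3.2.6, 4.2.7.8 | Not stated | Not stated |
| Best absolute change | 4.2.7.8 | Not stated | Not stated |
| PFS | 3.2.1 | No, declared explicitly | Progression is the event |

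**Step 2. Can scans after a switch exist?** Yes. Before protocol version 2.0, SAP 3.1 continues scanning after study drug stops and after new therapy starts. Scans after progression can exist too, because 3.1 continues treatment from first progression to a confirmatory scan.

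**Step 3. Does another section remove them?** No. SAP 4.1.3 names target lesion size and asks for exhaustive visit windows. Its on-treatment limit applies only to maximum and minimum summaries. SAP 2.1.1 presents efficacy by randomised arm whatever treatment was received. By contrast, 3.3.3, 3.3.4 and 3.3.6 limit change from baseline in safety variables to visits on treatment, so the SAP writes such limits where it wants them.

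**Step 4. Size.** The relevant contrast is the visit mean as planned against the visit mean with the filter. The filter removes the patient from that visit, and SAP 4.1.4 does not in general impute missing values. Let n be the patients with data at the visit, x the change of the one patient scanned after switching, and m the mean of the other n - 1.

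- Mean as planned: (x + (n - 1)m)/n
- Mean with the filter: m
- Difference: (x - m)/n

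The SAP gives none of these values. Assume n = 12, which is plausible with 29 patients planned 1:1, and x = -40%:

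- m = 0: (-40 - 0)/12 = -3.3 points
- m = -30: (-40 + 30)/12 = -0.8 points
- m = -40: (-40 + 40)/12 = 0
- m = -50: (-40 + 50)/12 = +0.8 points

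If nobody is scanned after a switch, the difference is zero.

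**Step 5. By-visit value against best value.** Suppose a patient's lowest change before switching is +10% and the change after switching is -40% (assumed values). The reported best percentage change is +10%, while the by-visit table carries -40%.

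**The case against.** The strongest reply is that using all collected data by randomised arm is a legitimate treatment-policy summary. SAP 2.1.1 sets that frame for efficacy, 3.2.1 counts PFS events regardless of later therapy, and DoR (3.2.3) follows PFS. This stands in part: not every efficacy variable is cut, and an all-data table would be acceptable if it were declared. But 3.2.1 declares the choice for PFS, whereas 3.2.6 and 4.2.7.8 declare nothing for by-visit change and apply the opposite rule to the best value of the same measure.

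The reply that exposure is narrow stands fully. After approval of protocol version 2.0, Group A has no scans, and Group B is scanned only to progression or for 3 months after discontinuation (3.1, 3.2). SAP 4.1.3 tabulates a visit only where at least 10 subjects in either group have data, so later visits, where scans after a switch would mostly fall, may not be shown. Efficacy is exploratory and no hypothesis is tested (section 4).

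A reader might go further and infer that the table credits a later drug's effect to the randomised arm and so always overstates shrinkage. The documents do not support that. Presentation by arm is not a claim of drug effect, and relative to the filtered table the direction depends on m, which is unknown. Nor is the shift the patient's own swing divided by n. For an assumed move from +10% to -40%, that would be -50/12 = -4.2 points, but the filter drops the patient and does not restore +10%.

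**Conclusion.** The inconsistency is real. As written, the plan puts scans into the by-visit table that it rejects for best percentage change, ORR and best overall response, and no other section filters them out. Best absolute change has no stated rule at all.

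The size cannot be determined from the SAP. Under the assumed n = 12 and x = -40%, one patient changes a visit mean by -3.3 to +0.8 points for m between 0 and -50%. The number of patients scanned after a switch is not given and may be zero.

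This is a minor correction to an exploratory, descriptive output. It touches only scans made after a switch, at visits that pass the display rule. The safety objective, PFS, ORR and best overall response do not change.

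**What to change.** In SAP 3.2.6 and 4.2.7.8, state that by-visit absolute and percentage changes, and best absolute change, use only assessments before the start of subsequent anti-cancer therapy. Later values are listed and flagged.

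In the same place, state explicitly whether by-visit values also stop at progression. Best percentage change, ORR and best overall response do, so a cut at subsequent therapy alone would not fully align the outputs.

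The cost is one sentence in the SAP and one filter in the program. The downside is slightly fewer values at later visits.

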4.2.8 Safety outcomes

The Safety Analysis Set will be used for all safety and tolerability tables, figures and listings except where expressly noted.

4.2.8.1 Adverse events

All AEs, both in terms of MedDRA PT and CTCAE grade, will be listed and summarized descriptively by count (n) and percentage (%) for each treatment group. MedDRA will be used for coding. Any AE occurring before study treatment (i.e., before Study Day 1) will be included in the AE listings, but will not be included in the summary tables (unless otherwise stated). These will be referred to as 'pre-treatment'. The summary tables will include all AEs that occurred after the start of treatment up until the end of the follow-up period.

All reported AEs will be listed along with the date of onset, date of resolution (if AE is resolved), investigator's assessment of severity and relationship to study drug. Frequencies and percentages of subjects reporting each preferred term will be presented (i.e., multiple events per subject will not be accounted for apart from on the episode level summaries).

Summary information (the number and percent of subjects by treatment) will be tabulated for:

- All AEs
- All AEs causally related to study treatment

- AEs with CTCAE grade 3 or higher
- AEs with CTCAE grade 3 or higher, causally related to study treatment
- Fatal AEs
- All SAEs
- AEs leading to discontinuation
- OAEs

An overall summary of the number and percentage of subjects in each category will be presented, as will an overall summary of the number of episodes in each category. In addition, a truncated AE table of the most common AEs, showing all events that occur in at least 5% of subjects overall will be summarized by preferred term, by decreasing frequency. This cut-off may be modified after review of the data.

AEs will be assigned CTCAE grades and summaries of the number and percentage of subjects will be provided by maximum reported CTCAE grade, SOC, PT and actual treatment group.

In addition, AEs with an outcome of death, SAEs, and OAEs will be listed.

4.2.8.2 AEs of special interest

Summary tables of AESIs will be produced. The number (%) of patients experiencing any of the specified terms will be presented overall, by maximum CTCAE grade, and by outcome.

4.2.8.3 Deaths

A summary of deaths will be provided with the number and percentage of subjects, categorized as:

- Related to disease under investigation,
- Fatal AE,
- Both related to disease under investigation and fatal AE,
- Fatal AE >30 days after last treatment dose,
- Deaths >30 days after last treatment dose, unrelated to AE or disease under investigation, and
- Subjects with unknown reason for death.

A corresponding listing will also be produced.

4.2.8.4 Laboratory evaluations

All laboratory data recorded in the eCRF will be listed. If any additional analytes to those in Table 5 are also recorded then these will be listed only.

All values will be classified as low (below range), normal (within range) and high (above range) based on reference ranges provided by the local or central laboratory. As applicable, values will be graded using CTCAE v4.0.

Plots of both the maximum post-baseline alanine transaminase (ALT) and aspartate transaminase (AST) versus the maximum post-baseline total bilirubin, expressed as multiples of their upper limit of reference range will be produced.

The laboratory variables to be summarised are shown in Table 3 below.

Table 3 Laboratory safety variables

Clinical chemistry (Serum/Plasma)	Hematology (Blood)	Urinalysis (Urine)
Albumin	Hemoglobin	Glucose
Alanine transaminase (ALT)	Leukocytes	Protein
Aspartate transaminase (AST)	Hematocrit	Blood
Alkaline phosphatase	Red blood cell (RBC) count	
Bilirubin, total	Absolute leukocyte differential count:	
Calcium, total	Neutrophils	
Creatinine	Lymphocytes	
Glucose	Monocytes	
Magnesium	Basophils	
Phosphate	Eosinophils	
Potassium	Platelet count	
Sodium	Reticulocytes	
Urea nitrogen/Blood urea nitrogen (BUN)		
TSH ¹		
Lactate dehydrogenase (LDH) ²		
Hepatitis B surface antigen ²		
Hepatitis C antibody ²		
Human immunodeficiency virus (HIV) antibody ²		
Activated partial thromboplastin time ²		
International normalised ratio ²		

¹ Free T3 and Free T4 to be measured only if TSH is abnormal.

² measured at the screening visit only

4.2.8.5 Vital signs (pulse and BP) and weight

All vital signs data will be listed. Absolute and percentage change from baseline for pulse, BP and weight will be summarized by treatment group, overall and by visit.

4.2.8.6 Physical examination

Abnormalities identified from physical examination will be listed.

4.2.8.7 ECG

All ECG data received will be presented in data listings. QTc summaries will be presented for subjects in the Safety Analysis Set. The ECG parameters that will be summarized (absolute values, change and percentage change from baseline) are: QTcF, RR, PR, QRS and QT.

The observed values and change from baseline in QTcF will be summarized by visit using summary statistics.

QTc outliers are defined as QTcF values following dosing that are greater than 450 ms or are increases from baseline greater than 30 ms. QTcF outliers will be highlighted in the data listings and summarized using the following categories:

- Values >450 ms, >480 ms, >500 ms
- Increase from baseline of >30 ms, increase from baseline of >60 ms, increase from baseline of >90 ms,
- Values >450 ms and increases of >30 ms. Values >500 ms and increases of >60 ms.

The number and percentage of subjects who meet the ECG outlier criteria at any assessment post-date of first dose will be summarized.

4.2.8.8 Left ventricular ejection fraction (LVEF)

Abnormal LVEF are defined as values less than the lower limit of normal. LVEF outliers and abnormal values will be highlighted in the data listings and LVEF will be summarized.

Further, subjects with outliers that are associated with an AE (related or unrelated to AZD9291) will be listed and summarized as appropriate, along with the duration of the abnormality.

4.2.8.9 WHO performance status

WHO performance status will be listed.

4.3 PK, pharmacodynamics and immunogenicity summary

AZD9291, MEDI4736 and metabolites AZ5104 and AZ7550 PK concentrations will be summarised. AZD9291 and MEDI4736 concentrations will be plotted using box-blots. Individual concentrations and ratios of metabolites will be listed.

ADA concentrations will be summarised and listed.

5. INTERIM ANALYSES

No interim analysis is planned.

6. CHANGES FROM PROTOCOL

OS is defined as the time from the date of randomisation until death due to any cause, whereas in the CSP it is defined as the time from the date of first dose until death due to any cause. As this is a randomised study the principle that efficacy analyses are measured from the date of randomisation is adhered to.

8. APPENDIX

N/A.
